9 INVESTIGATIONAL PLAN

9.1 Overall Study Design and Plan

9.1.1 Description

This is a Phase II, randomised, multi-centre, double-blind, placebo-controlled proof-of-concept study to assess the safety, tolerability and efficacy of oral Xanamem™ QD in adult subjects with mild dementia due to AD.

It is planned to randomise approximately 174 subjects at approximately 20 study sites in three countries (Australia, UK, and USA), with the aim to enrol 7 to 10 subjects at each study site. Subject enrolment will be competitive but a cap of 20 subjects per study site is to be established to avoid any site effects. In case data quality at one study site is creating concerns, an enrolment stop can also occur at fewer than 20 subjects.

The DSMB will periodically meet for the review of accumulating safety study data and will also be involved in the interim efficacy analysis (see [Section 15.2.4](#) for details).

At the Baseline visit (Week 0), eligible subjects will be randomised on a 1:1 ratio to receive either Xanamem™ administered orally, QD (treatment group) or matching placebo (placebo group). Subjects will return to the study site for the Interim visits (Week 4 and Week 8), EOT (Week 12) and Follow-up (4 weeks post last dose of study drug) visits, at which study assessments, as detailed in [Table 1](#) (Schedule of Assessments), will be performed. For further details on the dosing and treatment of subjects, refer to [Section 10](#).

Ad hoc telephone contact may occur at any time-point throughout the study, if deemed necessary by the investigator/study nurse, or if the subject wishes to report an AE.

Subjects will be interviewed and examined at the study site at each visit, and will complete a variety of questionnaires and routine safety evaluations.

Selected subjects will undergo additional PD sampling at specific visits after providing appropriate informed consent. Subjects who do not provide consent for this optional assessment, will still be eligible for the main study.

The overall study duration for an individual subject will be 17 to 20 weeks, including a screening period of 1 to 4 weeks, a double-blind treatment period of 12 weeks, and a follow-up period of 4 weeks. The total duration of the study is expected to be approximately 2 years (last subject last visit).

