9.2.2 Risk/Benefit and Ethical Assessment

Xanamem™'s mechanism of action suggests a main role on hippocampal function, which may improve amnesic symptoms that are the main symptoms in subjects of mild AD. Furthermore, Xanamem™ may slow the progression of amyloid plaque deposition in the brain. Therefore, Xanamem™ has the potential for both symptomatic and disease-modifying effects in subject with mild AD.

Xanamem™ is an inhibitor of the 11β -HSD1 enzyme. Compounds which inhibit 11β -HSD1 are intended to affect the intracellular cortisone-cortisol balance, resulting in altered glucocorticoid action. It is therefore expected that AEs seen following the administration of Xanamem™ may be related to effects on glucose and fatty acid metabolism, or loss of suppression of innate immunity. In addition, inhibition of 11β -HSD1 results in enhanced cortisol clearance and potentially a compensatory increase in ACTH and cortisol secretion to maintain normal cortisol levels. As a result, ACTH-dependent secretion of adrenal androgens may be increased.

To date, Xanamem™ has an acceptable safety profile: in the MAD study²², all treatment-emergent AEs (TEAEs) were either mild or moderate in intensity. A total of 6/24 (25.0%) subjects reported at least one TEAE possibly related to study drug, whilst all the other TEAEs were reported as unrelated or unlikely to be related to study drug.

Of the five TEAEs considered to be moderate in intensity, one event of diarrhoea (20 mg UE2343) and one event of headache (35 mg UE2343) were considered as possibly related to study drug. The other moderate TEAEs were all unrelated or unlikely to be related to study drug. The laboratory parameters were within normal range and no clinically significant abnormalities were recorded. In the subsequent fed-fasted study²² in 12 subjects, the most commonly reported TEAE by preferred term was "Abnormal dreams", with a total of

five events reported by 5/12 (41.7%) subjects. These were considered possibly related to study drug (two events under fed conditions, one under fasted conditions and two across both the fed and fasted period), all mild in intensity and resolved.

Overall, there were no clinically significant abnormalities noted in nerve conduction studies for any of the subjects in the MAD cohorts.

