- **Optional PD assessment.** Samples for the determination of ACTH, DHEAS, androstenedione and testosterone will be taken from a sub-population of approximately 50 subjects enrolled into the main study, who also volunteer to take part in the PD sub-study, unless a higher number is defined as a result of the analysis of the data from those subjects, by the DSMB. Subjects who cannot provide a PK sample will not undergo PD sampling. Another attempt for PD sampling will be made at the next visit. The objective of this is to assess the impact of Xanamem™ on the hypothalamic-pituitary-adrenal axis. The sample must be taken pre-dose (as early as possible in the morning). For optimal results, the sample for androstenedione analysis

should be taken between 6 am and 10 am. PD results are blinded and will not be provided to the sites or the subjects; results will not be disclosed to study sites to avoid unintended subject treatment unblinding.

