3.4 Randomisation and Blinding

This study is randomised, double-blind, placebo-controlled Phase II proof-of-concept study. There is a well-defined randomisation plan for subject's randomisation and blinding. Detailed randomisation details will be document in the study randomisation plan. The randomisation codes will be computer-generated by ICON Biostatistics, and kept by a statistician independent from the project team. A copy will be provided to whoever performs the PK and PD assessments, when the Pharmacokinetic (PK) and Pharmacodynamic (PD) data are analysed, as well as to the DSMB (Data Safety Monitoring Board). Randomisation codes will be generated in blocks stratified by site to ensure approximate balance between dose schemes (1:1) and balanced per site.

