5.0 STATISTICAL CONSIDERATIONS

5.1 General Considerations

Statistical analyses will be performed using SAS software, version 9.3 or higher. Formal hypothesis will be tested in this study and it will be explained in detail on following section.

Continuous data will be summarized using number (n), mean, standard deviation (SD), minimum value, median, maximum value and, if appropriate, number of missing values. Unless noted otherwise, summaries will be produced by visit (where applicable) and results will be presented overall and by treatment group. If more than one value is reported at a scheduled visit, the value collected closest to the intended visit date will be used. In the case of a tie, the latest version will be summarized. If there is more than one value reported at the same date, the average value of multiple values will be obtained. Where changes from Baseline are analysed, subjects will be included only if both a Baseline and at least one valid post-Baseline measurement are available.

Categorical data will be summarized using number (n) and percentages. Percentages will be calculated based on the number of non-missing values (if result display by visit) otherwise it will be calculated based on the population count. The number of missing values will be presented as a separate category with no percentage, if one or more subjects have missing data for the summary. Otherwise, all categories will be presented (even if no subjects are counted in the category). Counts of zero in any category will be presented without percentage.

Precision of summary statistics:

- Integer – Sample size (n, N) and number of missing responses (if displayed).
- One additional decimal place than reported/collected on the electronic Case Report Form (eCRF) – mean and median
- Two additional decimal places than reported/collected on the eCRF – standard deviation.
- Same number of decimal places as reported/collected on the eCRF – minimum, maximum.
- Percentages, CV – one decimal place.
- P-values will be presented for three decimal points (i.e., 0.xxx).

Precision of output display:

- Report output will be generated using SAS (version 9.3 or higher) ODS RTF with no borders or framing around table elements.
- Font – Courier New font with minimum of eight point font size
- Margins – For USA, minimum of 3/4” bound edge margin and 3/8” other margins on 8.5”x11” paper.

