7.9 Pharmacokinetics (PK) /Pharmacodynamics (PD) Endpoints Analyses

PK plasma and PD parameters will be assessed using the PK/ PD set, respectively.

A separate Modelling and Simulation Analysis Plan will be prepared and results from the PK/PD modelling will be reported separately from the clinical study report.

XanamemTM concentrations will be summarized descriptively by treatment group, visit and time point.

PD parameters of ACTH, DHEAS, androstenedione and testosterone will be summarized for absolute values, change from baseline and % change from baseline.

Sub-group analysis will be performed by gender for PK/PD data. PK/PD data sampling details will be listed.

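### The PD hormone sub-study is meant to assess the drug's impact on the HPA axis, but the SAP plans only by-arm summaries, with no Xanamem-versus-placebo estimate or interval, and one of them (mean % change) is biased upward

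*Protocol*

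**What the plan says.** Protocol section 13 states the purpose of the optional PD samples: "The objective of this is to assess the impact of Xanamem™ on the hypothalamic-pituitary-adrenal axis". The samples are "taken from a sub-population of approximately 50 subjects enrolled into the main study", all of them volunteers, and the DSMB may raise that number. They are drawn at Baseline, Weeks 4, 8 and 12, and Follow-up. Protocol 9.2.2 gives the expected direction. After describing a possible compensatory rise in ACTH and cortisol secretion, it adds: "As a result, ACTH-dependent secretion of adrenal androgens may be increased".

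The planned analysis is in SAP 7.9: "PD parameters of ACTH, DHEAS, androstenedione and testosterone will be summarized for absolute values, change from baseline and % change from baseline". A subgroup analysis by gender is added. SAP 5.1 supplies the default statistics: "Continuous data will be summarized using number (n), mean, standard deviation (SD), minimum value, median, maximum value". It also sets the layout: "summaries will be produced by visit (where applicable) and results will be presented overall and by treatment group".

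No other section supplies a between-arm estimate for these hormones. Protocol 15.2.3 gives no PD-specific method. Its PK/PD modelling paragraph (15.2.3.8) describes population PK and an optional exposure-response step using exposure and efficacy or safety endpoints. SAP 7.12 leaves cortisol and unspecified further analyses to a separate post-lock document.

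**The concern.** The stated aim is causal and the trial has a randomised placebo arm, so the natural output is a Xanamem-versus-placebo contrast with an interval. The plan uses such contrasts elsewhere. Each secondary efficacy scale gets an exploratory ANCOVA between arms (Protocol 15.2.3.6, SAP 7.7.2), and Protocol 15.2.3.7 calls for an exploratory comparison of the groups on nerve function. The PD hormones get neither.

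The choice of statistic adds to this. In a mean of individual % changes, a doubling counts +100% and a halving only -50%. Random variation alone therefore pushes the mean above zero. The protocol expects the drug to raise these hormones, so a noise-driven rise in the Xanamem column could be read as the predicted effect. Conversely, a real moderate rise could pass without comment if no interval shows what the data exclude.

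**Working it through.** **Inputs.** About 50 PD subjects (Protocol section 13). Allocation: "eligible subjects will be randomised on a 1:1 ratio" (Protocol 9.1.1), which gives about 25 per arm in expectation. The documents give no variability for the hormones and no power or precision basis for the 50; Protocol 15.1 covers only ADAS-Cog v14 and nerve function. There is therefore no PD figure to reproduce. The SD *s* of the within-subject log ratio (follow-up/baseline) is assumed to be 0.3, 0.5 or 0.7.

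**Step 1: mean % change with no drug effect.** If the log ratio is normal with mean 0 and SD *s*, the expected ratio is exp(s²/2), so the expected mean % change is exp(s²/2) − 1. With independent errors at the two visits this equals CV², where CV is the within-subject coefficient of variation.

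**Step 2: precision of the missing contrast.** With n = 25 per arm, the 95% CI for the Xanamem/placebo geometric mean ratio (from log change) is the estimate multiplied and divided by exp(t × s × √(2/25)), with t(0.975, 48 df) = 2.011 and √(2/25) = 0.283.

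| s (assumed) | implied CV | expected mean % change, no effect | 95% CI factor |
|---|---|---|---|
| 0.3 | 21% | exp(0.045) − 1 = +4.6% | 1.19 |
| 0.5 | 36% | exp(0.125) − 1 = +13.3% | 1.33 |
| 0.7 | 53% | exp(0.245) − 1 = +27.8% | 1.49 |

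**Step 3: which summaries are affected.** In 20,000 simulated trials with 25 per arm, log-normal values and no effect, both arms had a positive mean % change in 56%, 69%, 79% and 86% of trials at CVs of 20%, 30%, 40% and 50%. An unbiased summary would give 25%. Across CVs of 15% to 60% the mean absolute change was about 0, the median % change averaged 0.2% to 1.6%, and the between-arm difference in mean % change was about 0. The bias therefore sits in one statistic and cancels between arms under no effect. With a true ratio θ it does not fully cancel: the difference in expected mean % change is (θ − 1) × exp(s²/2). At θ = 1.4 and s = 0.5 this is 0.40 × 1.133 = 45 percentage points instead of 40.

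**Step 4: gain from baseline adjustment.** With equal variances and baseline correlation r, the ratio of ANCOVA to change-score variance is (1 + r)/2. At an assumed r = 0.5 this is 0.75. For s = 0.5 the half-width on the log scale falls from 0.284 to 0.284 × √0.75 = 0.246, so the CI factor goes from 1.33 to about 1.28. In simulation at this single setting, with a true 1.4-fold rise and a one-sided 5% test, power was about 72% for % change, 76% for log change and 85% for log-scale ANCOVA. Most of the gain comes from the baseline adjustment.

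**Step 5: uneven volunteers.** Stratification is by site only: "Randomisation codes will be generated in blocks stratified by site to ensure approximate balance between dose schemes (1:1) and balanced per site". PD participation is not a stratum. Under simple randomisation, 18 to 32 of 50 would be on Xanamem in 95% of cases. At 18 versus 32, √(1/18 + 1/32) = 0.295 and the factor at s = 0.5 is exp(2.011 × 0.5 × 0.295) = 1.35, so precision barely changes.

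**The case against.** Much of the case on the other side stands.

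- **Placebo is in the tables.** A reader might infer that the Xanamem arm must be judged on its own change. SAP 5.1 says otherwise: results are shown by arm and visit, with n, mean, SD and median. An unadjusted difference and interval can be worked out from those. What cannot be recovered is a baseline-adjusted, log-scale estimate.
- **The bias is narrow.** It affects only the arithmetic mean % change. The absolute change and the median are planned too. The word arithmetic is not in SAP 7.9; it follows from the SAP 5.1 default.
- **Other HPA data exist.** A reader might infer that about 50 volunteers are the only evidence on this risk. They are not. Cortisol is assayed from the PK samples planned for all enrolled subjects (Protocol 8.5, Table 1 footnotes, section 13), with its analysis deferred under SAP 7.12. The PD data are also described as complementing Phase I (Protocol 9.2, 15.2.4).
- **The gender tables are no fault.** They come in addition to the full-sample summary and do not replace it.
- **A modelling plan exists but is not part of these documents.** The protocol's outline of it does not promise this comparison; its content cannot be confirmed.
- **Standing and multiplicity.** The sub-study is optional, lies outside the primary and secondary objectives, and is reported descriptively like the laboratory and metabolic data. Four hormones at three visits give 12 intervals. If they were independent, the chance that at least one excludes 1 under no effect would be 1 − 0.95¹² = 46%.

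**Conclusion.** The point holds as a gap between objective and analysis. For the four hormones the plan provides no estimate of the drug's effect with its uncertainty, although the aim is to assess that effect. One planned statistic leans in the predicted direction by about +5% to +28% under no effect. That range rests on an assumed log-ratio SD of 0.3 to 0.7, on log-normal values and, for the precision figures, on about 25 subjects per arm.

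The stronger conclusion, that the sub-study leaves its objective wholly unanswered, is not supported. The arms can be compared by eye or by a crude calculation, and cortisol is measured separately. Severity is minor: no primary result, secondary result or efficacy stopping boundary depends on it.

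**What to change.** In SAP 7.9 add, for each of the four hormones at Weeks 4, 8 and 12, an ANCOVA of log(value) on treatment, log(baseline) and sex, labelled exploratory. Report the Xanamem/placebo geometric mean ratio with its 95% CI. Replace the arithmetic mean % change with the geometric mean ratio to baseline. Keep the by-gender and Follow-up summaries as descriptive tables.

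The cost is a paragraph of SAP text and a few tables. All samples are already scheduled. The 12 intervals carry no multiplicity control, and the SAP should say so, so that one isolated interval excluding 1 is not read as confirmed.

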14 OTHER EXPLORATORY ASSESSMENTS

Other exploratory assessments will include:

- **Metabolic function** (lipids, blood pressure, glucose, HbA1c, body weight and BMI) analysis will be performed on all enrolled subjects.

The timing and frequency of this assessment is described in [Section 9.4](#) and [Section 9.4.1](#).

15 STATISTICAL EVALUATION

15.1 Sample Size and Power

The sample size calculation is based on ADAS-Cog v14 rather than ADCOMs as prior information on the treatment effect to be anticipated in the ADCOMs scale is very limited. The sample size at a one-sided type I error rate of 5% and a power of 80% for detecting a difference of 2 points in the change from Baseline between the treatment groups is 78 subjects per arm, if the standard deviation of the change from Baseline is 5 points. It is planned to include ADAS-Cog v14 into the confirmatory testing stream by the use of a hierarchical testing procedure, such that no adjustment of the type I error rate is necessary.

As a drop-out rate of approximately 10% is assumed, the number of subjects randomised should be increased to approximately 174 (87 per treatment group).

Regarding NFM, the sample size of 156 subjects (approximately 78 subjects per treatment group) is sufficient to ensure that any untoward effects with a true proportion of at least 3% are observed in at least one subject within a treatment group with a probability of approximately 90%. An untoward effect with a true proportion of 5% or higher will be detected with a probability of > 98% in a sample of 78 subjects.

The study is planned to enrol 7 to 10 subjects at each study site.

15.2 Statistical Methods

15.2.1 Statistical Analysis Sets

Safety Analysis Set

The safety analysis set will consist of all subjects who received at least one dose of study drug. Subjects will be analysed according to the treatment they actually received.

The safety analysis set will be the primary analysis set for safety analyses.

Full Analysis Set

The full analysis set (FAS) will consist of all subjects randomised who received at least one dose of study drug. Subjects will be analysed in the treatment group they were randomised to even if they received incorrect study drug. Where changes from Baseline are analysed, subjects will be included only if both a Baseline and at least one valid post-Baseline measurement are available.

The FAS will be the primary analysis set for efficacy analyses.

Per Protocol Analysis Set

The per protocol (PP) analysis set is a subset of the FAS, and will consist of all randomised subjects for whom no key protocol violation is documented (refer to the applicable ICON standard operating procedure [SOP]). The PP analysis set will provide supportive data for the efficacy analyses.

Allocation of subjects to the PP analysis set will be performed before unblinding of the study.

PK Set

The PK set will consist of all subjects in the safety population who have at least one post-dose PK assessment. PK analyses will be performed using the PK set.

PD Set

The PD set will consist of all subjects in the safety population who have at least one post-dose PD assessment. PD analyses will be performed using the PD set.

15.2.2 Efficacy and Safety Variables

15.2.2.1 Primary Efficacy Variables

The primary objective of this study will be evaluated using two primary efficacy variables.

The first primary efficacy variable is the change from Baseline (Week 0) to Week 12/EOT in the ADCOMs, a composite score based on ADAS-Cog v14, CDR-SOB and MMSE.

The second primary efficacy variable is the change from Baseline (Week 0) to Week 12/EOT in the ADAS-Cog v14.

Multiplicity between both primary endpoints will be handled using an a priori hierarchical approach, such that the results for the ADAS-Cog v14 will only be interpreted in a confirmatory fashion if results for the ADCOMs allowed a rejection of the null hypothesis.

15.2.2.2 Secondary Efficacy Variables

The following secondary efficacy variables will be evaluated:

- RAVLT
- CDR -SOB
- MMSE
- NPI
- NTB – Executive Domain (COWAT and CFT)

15.2.2.3 Safety Variables

The following safety variables will be evaluated:

- Clinical safety laboratory values
- AEs, SAEs and AESIs
- ECG
- NFM:
 - NTSS-6
 - TCNS
 - NCV and amplitude of peripheral motor and sensory nerves
- CSSRS

- Physical examination
- Vital signs

15.2.2.4 PK and PD Variables

- PK assessment
- PD assessment: ACTH, DHEAS, androstenedione and testosterone

15.2.2.5 Other Exploratory Variables

- Metabolic function: lipids, blood pressure, glucose, HbA1c, body weight and BMI

15.2.3 Methods of Statistical Analyses

15.2.3.1 General Principles

The aim of the primary efficacy analysis is the evaluation of the performance of Xanamem™ as compared to placebo for the change in the primary efficacy endpoints ADCOMs and ADAS-Cog v14 from Baseline to Week 12/EOT. The two primary efficacy variables will be evaluated in an a priori hierarchical fashion, where the results of the ADAS-Cog v14 analysis will only be interpreted as confirmatory if superiority of Xanamem™ over placebo can be shown for the ADCOMs.

The aim of the secondary efficacy analyses is to provide general results regarding the performance of Xanamem™ as compared to placebo in subjects with mild dementia due to AD.

A statistical analysis plan (SAP) will be prepared and finalised before study data are unblinded. A separate Modelling and Simulation Analysis Plan will be prepared for PK data.

15.2.3.2 Missing Data

For efficacy variables where the change from baseline is analysed, no imputation for missing values will be performed, i.e. the analysis will be based on “Observed Cases”, except where otherwise specified.

Treatment of missing items for the individual scores will be described in the SAP.

Missing Baseline data for the MMSE may be replaced by the Screening results only for the analysis of MMSE alone. When MMSE results are analysed as part of the ADCOMs analysis, such a replacement is not allowed, in order to ensure that all Baseline values contributing to the ADCOMs refer to the same point in time.

Other replacement of missing values is not foreseen.

